Familial aggregation and inherited predisposition have been increasingly investigated in multiple cancer types. In breast, ovarian, prostate and colorectal malignancies, genetic counselling is recommended in patients showing risk criteria for syndromes of inherited susceptibility to cancer, as aggregations with other malignancies have been widely described within families of these patient populations [1–3].

With a predicted number of death of about 160 000 cases in 2023 in Europe and 127 070 in US [4,5], Non-Small Cell Lung Cancer (NSCLC) still remains a leading cause of cancer death worldwide. A positive smoking history represents the main cause related to NSCLC (90% of cases)[6], while environmental factors such as exposure to radon, asbestosis and air pollution have been linked to lung cancer among never smokers [7–9]. However, few studies have investigated the impact of a positive family history of cancer (FHC) in patients with NSCLC, describing types of other malignancies that can co-occur within relatives of patients with NSCLC. In previous reports, the relative risk (RR) of developing lung cancer directly correlated with the number of lung cancer cases in first-degree relatives y (RR= 2.57 for first-degree relative ≥ 1 to RR= 4.24 for first-degree relative affected ≥ 3), and a similar trend has been observed when taking into account second and third degrees [10]. Furthermore, RR of developing lung cancer has been estimated to be up to 1.89 among those having a first-degree relative with lung cancer as second primary malignancy [11]. However, all these studies were conducted using local national registry, with no additional info on potential within-families clustering of other risk factors, including tobacco smoking exposure and other geographical/epidemiological factors. In addition, retrospective approaches to this topic are heavily impacted by recall bias and misclassification [12–13].

More recently, a “high burden” of family history of cancer in patients with advanced stage NSCLC, has emerged as potential predictive factor for systemic treatment with PD-1/PD-L1 checkpoint inhibitors, but without showing enrichment of somatic DNA damage and repair (DDR) gene alterations in tumour samples [14]. In terms of germline genetic alterations, lung cancer risk has been associated with rare genetic syndromes such as the Li-Fraumeni syndrome [15]. Furthermore, in multiple genome-wide associations studies three main susceptibility loci have been associated with increased risk of developing NSCLC including 15q25, 5p15 and 6p21 regions, corresponding to *CHRNA3*, *CHRNA5*, and *CHRNBT4*, *TERT*, *CLPTM1L*, *APOM*, *BAG6* genes [7].

To underline the importance and the potential clinical implications of investigating FHC in patients with NSCLC, a recent retrospective study conducted in a cohort of 7,7888 patients with NSCLC, undergoing to commercially available genetic germline testing, but with no information about their FHC, pathogenic germline variants (PGV) or likely PGV were found in 14.9% of cases and an additional 2.9% of cases carried a single PGV in a gene associated with autosomal recessive inheritance. Among these 14.9% PGV positive, 61.3% of them had a PGV in DDR/HRR genes and 95.1% of them harboured a PGV in clinically actionable genes, with BRCA2 (2.8%),

CHEK2 (2.1%), ATM (1.9%), TP53 (1.3%), BRCA1 (1.2%), and EGFR (1.0%) being the most commonly reported PGVs [16].

Despite this few evidence, genetic causes of lung cancer still remain largely unknown, and FHC/potential within-family clustering of other risk factors need to be prospectively assessed.

With the aim of individuating and describing FHC and potential within-family clustering of other risk factors in patients with NSCLC the FAHIC – Lung study will represent the firsts prospective observational study in this area.

2 Study Objectives

2.1 Primary Objectives:

The primary objectives of this study will be:

- description of the FHC and potential within-family clusters of other risk factors among patients with NSCLC
- identification of potential FHC patterns and within-family clusters of other risk factors to address patient with NSCLC to systematic genetic counselling.

2.2 Secondary Objectives:

Secondary objectives include:

- description of clinic-pathological and oncological characteristics of patients with NSCLC of according to FHC patterns and within-family clusters of other risk factors.

3 Study design

3.1 General Design

This is a prospective, observational, multi-centre study. Our study population will be represented by consecutive patients with histologically diagnosed NSCLC, regardless of their age, TNM stage, smoking status, and other clinic-pathologic characteristics.

Patients' history will be carefully collected by investigators through a dedicated self-reported study questionnaire, which has been developed for the purpose of this study (provided as **Appendix 1**)

The ad-hoc study questionnaire has been validated by the genetic expert of the steering committee who will train each investigator to translate the returned questionnaire into standardized family trees. Study questionnaire will focus on:

- Family history of cancer;
- Type of tumours/primary tumour site among relatives with history of cancer;
- Age at diagnosis among relatives with history of cancer;
- Biological sex of relatives with history of cancer;

- Exposure to tobacco smoking and smoking habits among relatives with history of cancer;
- Geographical origin of participants and relatives with history of cancer;
- Personal history of multiple malignancies;
- Potential professional and environmental exposure to carcinogens of participants and relatives with history of cancer;
- Ethnicity of both participants and relatives with history of cancer.

To minimize risks of recalling bias, each patient will be given a minimum time of 4 weeks to gather family history information. The study-questionnaire will be then collected at the following clinical consultation as already planned per clinical practice, with no additional study-specific procedures.

During the first study visit all patient's clinic-pathologic will be collected and study participants will be given the ad-hoc questionnaire, which will be returned to the study personnel at the follow-up study visit.

The following clinic-pathologic characteristics will be collected:

- Smoking status (active/passive, package/year, total years of smoking)
- Eastern Cooperative Oncology Group Performance Status (ECOG-PS)
- Age at diagnosis;
- Tumour histology;
- Tumour stage at diagnosis according to the 8th edition of TNM staging system;
- Ethnicity;
- Professional and environmental exposure to carcinogens;
- Programmed death ligand-1 tumour proportion score (PD – L1 TPS)
- Any available oncogenic drivers including epidermal growth factor receptor (EGFR), Kirsten rat sarcoma virus (KRAS), BRAF, c-MET, mutations and Anaplastic lymphoma kinase (ALK), ROS-1, RET, neurotrophic tyrosine receptor kinase NTRK translocation/gene fusions.

Personal history of other synchronous/metachronous primary malignancies.

Study data will be collected through dedicated electronic case report form (e-CRF). A full list of information that will be collected through the dedicated eCRF (provided as **appendix 2**).

Even though no established FHC criteria exists to refer patients with NSCLC to a genetic counselling for germ-line testing, investigators will assess participant questionnaire at the follow-up study visit and refer patients to genetic counselling when clinically indicated as per local routine practice.

Following collection of participants' questionnaires, we will be able to reconstruct patients' family tree with additional information on how other potential risk factors, such as history of

smoking, exposure to professional/environmental carcinogens, segregate within the relatives with history of cancer.

We will be able to describe whether recurrent family clusters of malignancies/risk factors are specifically associated with risk of lung cancer in order to individuate patients to specifically address to systematic genetic counselling, to assess eligibility for germ-line testing in clinical practice. Secondly, we will also investigate distribution of participants clinic-pathologic characteristics to assess whether any patients and/or tumour-related feature is associated with patterns of FHC and within-family clustering of other risk factors.

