3.2 Participants Selection

Inclusion Criteria

[figure not shown]
- Histopathological diagnosis of Non-Small Cell Lung Cancer (all stages)
- Age ≥ 18 years old
- Signed informed consent
- Availability of familiar and/or personal anamnestic data of cancer

Exclusion Criteria

- Unavailability of familiar and/or personal anamnestic data of cancer
- Patient's refusal

3.3

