3.4 Study flow-chart

3.5 Study duration

The esteemed study duration is 24 months. Enrolment will start after protocol approval and will last for 12 months. Data analysis will last 12 months from the closure of data collection.

4 Statistical Plan and Sample Size

Given the descriptive nature of the study, and the lack of available data on the relationship between family history of cancer and NSCLC, the minimum sample size for the study has been established on the only study available to date which investigated distribution of FHC among unselected patients with stage IV NSCLC, which described a high familiar burden of cancer (i.e. especially enriched FHC with cases of cancer in both the collateral and lineal family lines) in up to the 6.8% of patients [14]. On the basis of this data, we hypothesized a prevalence of 10% of participants with an especially enriched family history of cancer in our study population; assuming a confidence level of 95% with a total width for the confidence interval of 0.1 (precision of +/- 5%) and considering a 10% drop out, the minimum number of study questionnaire to collect to properly describe the group of interest following a binomial “exact” calculation of the sample size is 175.

Descriptive statistics will be used as appropriate to report FHC data, distribution of within-family other risk factors and baseline clinic-pathologic characteristics. The Fisher exact test and the χ^2 test will be used as appropriate to compare categorical variables (e.g. distribution of baseline characteristics according to the personal/familial positive or negative history). Analyses were performed using the R-studio software, R Core Team (2021). R: A language and environment for statistical computing. R Foundation for Statistical Computing, Vienna, Austria, and the MedCalc® Statistical Software version 20 (MedCalc Software Ltd, Ostend, Belgium; <https://www.medcalc.org>; 2021).

5 Data Management and confidentiality

Data will be collected and retained in accordance with the European General Data Protection Regulation (GDPR) L119, 4 May 2016 and in compliance with other international data protection regulations, such as the title 21 CFR Part 11 of the Code of Federal Regulations, the Health Insurance Portability and Accountability Act of 1996 (HIPAA), and the United Kingdom GDPR.

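### Section 3.1 promises to describe association with lung cancer risk, but every participant has NSCLC and no comparison group or reference rate is planned

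*Combined protocol and SAP*

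**What the plan says.** After explaining how family trees will be built, section 3.1 says the study will describe "whether recurrent family clusters of malignancies/risk factors are specifically associated with risk of lung cancer in order to individuate patients" who should be sent for systematic genetic counselling. The rest of the plan is descriptive and confined to cases:

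- Section 3.2 requires the disease of everyone enrolled: "Histopathological diagnosis of Non-Small Cell Lung Cancer (all stages".
- Section 4 calls the study descriptive and sizes it on the precision of one proportion: "we hypothesized a prevalence of 10% of participants with an especially enriched family history of cancer in our study population".
- Section 4 plans descriptive statistics and Fisher exact or chi-square tests. Its example is the "distribution of baseline characteristics according to the personal/familial positive or negative history".
- Among the questionnaire topics, section 3.1 lists "Exposure to tobacco smoking and smoking habits among relatives with history of cancer" and "Potential professional and environmental exposure to carcinogens of participants and relatives with history of cancer". It later ties the risk-factor part of the family tree to relatives who have had cancer.
- Section 2.1 has two primary objectives. One is to describe family history and within-family risk-factor clusters in NSCLC patients. The other is to identify patterns and clusters that could point to genetic counselling.

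No section names controls, population rates or expected numbers of affected families.

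**The concern.** A statement about association with the risk of a disease needs people or families without that disease, or an expected rate from outside the study. This study has only NSCLC patients. If the sentence in section 3.1 stays, a pattern that is merely common among NSCLC families could be reported as a marker of lung cancer risk and cited in support of referral. The data would fit a raised, unchanged or lowered risk equally well. Recruiting more NSCLC patients would not help, because the quantity that is missing is never observed.

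A second, smaller matter depends on the questionnaire itself. If exposures are recorded only for relatives with cancer, the tree shows which exposures occur together among affected people. It cannot show whether an exposure is more frequent in affected than in unaffected relatives.

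**Working it through.** **The plan's own figure.** Inputs from section 4: expected proportion 10%, 95% confidence, total interval width 0.10, 10% dropout. The smallest n whose exact (Clopper-Pearson) interval is no wider than 0.10 is 158 (0.0580 to 0.1577, width 0.0997). It is 159 if the count is rounded to a whole number. Allowing for dropout:

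- 158/0.9 = 175.6, so 176; 159/0.9 = 176.7, so 177.
- 158 × 1.1 = 173.8, so 174; 159 × 1.1 = 174.9, so 175.

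The stated 175 is reproduced. It gives the precision of one proportion among cases and is not a basis for a comparison with people free of lung cancer.

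**What the study would observe.** 175 × 0.9 is about 157 evaluable forms. At 10%, about 16 participants have an enriched family history: 16/157 = 10.2%, exact 95% CI 5.9% to 16.0%.

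**What that implies for lung cancer risk.** Let q be the share of comparable people without lung cancer who have the same history. The documents give no q, so the values below are assumptions.

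Odds ratio = (0.10/0.90) / (q/(1 − q)), where 0.10/0.90 = 0.1111

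| Assumed q | q/(1 − q) | Odds ratio |
|---|---|---|
| 5% | 0.0526 | 2.11 |
| 7.5% | 0.0811 | 1.37 |
| 10% | 0.1111 | 1.00 |
| 15% | 0.1765 | 0.63 |

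The same 16 of 157 goes with every row. The confidence interval covers sampling error in the case proportion only and says nothing about q. The earlier figure that section 4 starts from (6.8%) also comes from NSCLC patients, so it cannot stand in for q.

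**Tests among cases.** Comparing history-positive with history-negative participants shows whether family history goes with patient or tumour features. Both groups have NSCLC, so no such test speaks to the risk of getting it.

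**Secondary point, if exposures are recorded only for affected relatives.** Assume 30% of relatives smoke, a cancer relative risk of 2 for smokers and 15% overall cancer risk.

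- Smokers among affected relatives: 0.30 × 2 / (0.30 × 2 + 0.70) = 0.60/1.30 = 46%.
- With 46% smokers overall and relative risk 1, the figure is again 46%.
- The two cases differ only in unaffected relatives. In the first, cancer risk in non-smokers is 0.15/1.30 = 0.115 and in smokers 0.231, so 0.30 × 0.769/0.85 = 27% of the unaffected smoke. In the second it is 46%.

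Families with no affected relative would give no relative-level exposure data. With k relatives counted and independent risk r each, their share is (1 − r)^k. At an assumed r of 15% this is 52% for k = 4 and 7% for k = 16. Over r from 10% to 20% it runs from 66% (k = 4, r = 10%) to 3% (k = 16, r = 20%). Independence is itself doubtful in a study of familial aggregation. The range is too wide to predict the number, so it should be counted and reported.

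**The case against.** The strongest reply is that the study is descriptive by its own account, that section 4 plans no risk estimate, and that one loose sentence does not change the design. That is largely right, and it limits the point to wording. It does not save the sentence, which names association with lung cancer risk and attaches a clinical use to it.

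A reader might go further in several ways that the documents do not support:

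- **That the primary objectives exceed the data.** The first is a description among NSCLC patients, which the data can serve. The second does not mention lung cancer risk, and identifying which NSCLC patients might be considered for counselling is a question among cases.
- **That the history-positive versus history-negative comparison is the only one planned.** Section 4 gives it as an example. Any other comparison would still be among cases, so the conclusion is the same.
- **That unaffected relatives are certainly left out.** Section 3.1 says what the questionnaire focuses on, which need not be a full list. Appendices 1 and 2 hold the form and the data list, and they were not in the text available for this review. Section 3.1 also states for itself that risk factors are followed within relatives who have had cancer, so the plan does not clearly claim more.
- **That participants' care rests on the disputed inference.** Section 3.1 leaves referral during the study to clinical indication under local practice.

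The relative risks cited in the introduction do not fill the gap either. The plan does not say that they will be used as a reference, and they are not the prevalence of an enriched history in people without lung cancer.

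**Conclusion.** The point holds for the sentence in section 3.1. With cases only and no reference rate, the study cannot show that family clusters are associated with lung cancer risk. At the plan's 10%, the implied odds ratio moves from 2.1 to 0.6 as the unobserved comparator share moves from 5% to 15%. Those shares are assumed, but the conclusion does not depend on them: it follows from the inclusion criterion and the absence of any comparator.

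The point about relatives' exposures is secondary and conditional on Appendix 1. Its figures are illustrations under stated assumptions. The description of family history is not touched, and 175 remains a sound size for the proportion that it was built for.

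**What to change.** In section 3.1, replace the sentence on lung cancer risk with wording such as:

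> We will describe recurrent patterns of malignancies, and of risk factors among participants and relatives with cancer, in patients with NSCLC; without a comparison group, no association with lung cancer risk will be inferred.

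Then check Appendix 1. If it records exposures only for relatives with cancer, add to section 4 that risk-factor clusters will be reported as co-occurrence among participants and affected relatives. Add also that the number of families with no affected relative will be given, because they contribute no relative-level exposure data.

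The cost is a few lines of text and one reported count. No extra patients, visits or data items are needed. The downside is a more modest stated aim. Recording exposures in unaffected relatives is not required here, and would not by itself support a claim about lung cancer risk.

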3.2 Participants Selection

Inclusion Criteria

[figure not shown]
- Histopathological diagnosis of Non-Small Cell Lung Cancer (all stages)
- Age ≥ 18 years old
- Signed informed consent
- Availability of familiar and/or personal anamnestic data of cancer

Exclusion Criteria

- Unavailability of familiar and/or personal anamnestic data of cancer
- Patient's refusal

3.3

3.4 Study flow-chart

3.5 Study duration

The esteemed study duration is 24 months. Enrolment will start after protocol approval and will last for 12 months. Data analysis will last 12 months from the closure of data collection.

4 Statistical Plan and Sample Size

Given the descriptive nature of the study, and the lack of available data on the relationship between family history of cancer and NSCLC, the minimum sample size for the study has been established on the only study available to date which investigated distribution of FHC among unselected patients with stage IV NSCLC, which described a high familiar burden of cancer (i.e. especially enriched FHC with cases of cancer in both the collateral and lineal family lines) in up to the 6.8% of patients [14]. On the basis of this data, we hypothesized a prevalence of 10% of participants with an especially enriched family history of cancer in our study population; assuming a confidence level of 95% with a total width for the confidence interval of 0.1 (precision of +/- 5%) and considering a 10% drop out, the minimum number of study questionnaire to collect to properly describe the group of interest following a binomial “exact” calculation of the sample size is 175.

Descriptive statistics will be used as appropriate to report FHC data, distribution of within-family other risk factors and baseline clinic-pathologic characteristics. The Fisher exact test and the χ^2 test will be used as appropriate to compare categorical variables (e.g. distribution of baseline characteristics according to the personal/familial positive or negative history). Analyses were performed using the R-studio software, R Core Team (2021). R: A language and environment for statistical computing. R Foundation for Statistical Computing, Vienna, Austria, and the MedCalc® Statistical Software version 20 (MedCalc Software Ltd, Ostend, Belgium; <https://www.medcalc.org>; 2021).

5 Data Management and confidentiality

Data will be collected and retained in accordance with the European General Data Protection Regulation (GDPR) L119, 4 May 2016 and in compliance with other international data protection regulations, such as the title 21 CFR Part 11 of the Code of Federal Regulations, the Health Insurance Portability and Accountability Act of 1996 (HIPAA), and the United Kingdom GDPR.

Data will be collected by investigators at each participating site through a dedicated electronic case report form (eCRF) designed by the study staff with the Research Electronic Data Capture software (REDCap, Vanderbilt University, Nashville, TN, USA) using a GDPR-compliant secure server at the coordinating center (Fondazione Policlinico Universitario Campus Bio-Medico, Rome, Italy) and will be kept for 5 years after the study completion.

Access to the database will be given to authorized personnel only at each site, log of access will be kept in the study file by the Principal Investigator with a secure two factor authentication system for each investigator.

A unique reference number will be assigned to each institution and a second-level unique and sequential ID number will be assigned to each participant.

Each participating institution will ensure that all anamnestic, clinical and follow-up information will be collected after a complete anonymization process. Investigators at the coordinating center (Fondazione Policlinico Universitario Campus Bio-Medico, Rome, Italy) will not be able to match participants' ID with potentially identifiable information, which will be accessible to local investigators only at each participating site.

Principal Investigator will ensure that the patient's privacy is maintained at all times. On the Case Report Form (CRF) or other documents, patients will be identified by a study ID number only.

Technical and organizational measures to ensure data protection will include: anonymization and encryption, confidentiality, integrity, availability and resilience of processes and services on a permanent basis, procedures for regularly testing, verifying and evaluating the effectiveness of technical and organizational measures in order to guarantee the security of the processing.

The investigator shall permit direct access to study source document for the purposes of monitoring, auditing, or inspection by the Sponsor, authorized representatives of the Sponsor and Regulatory Authorities.

6 Ethical consideration

The study will be conducted in accordance with the principles of Good Medical Practice and the recommendations for physicians involved in research on human subjects adopted by the 18th World Medical Assembly, Helsinki 1964 and later revisions.

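### Does the 24-month timetable leave too little time for the last questionnaires, and does the plan need a rule for forms that never come back?

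*Combined protocol and SAP*

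**What the plan says.** Section 3.5 gives the total ("The esteemed study duration is 24 months") and its two parts: "Enrolment will start after protocol approval and will last for 12 months. Data analysis will last 12 months from the closure of data collection".

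Section 3.1 sets the timing for the questionnaire, which is the source of the primary data. At the first study visit, "clinic-pathologic will be collected and study participants will be given the ad-hoc questionnaire". After that, "each patient will be given a minimum time of 4 weeks to gather family history information", and the form "will be then collected at the following clinical consultation as already planned per clinical practice". No upper limit is put on that wait.

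Section 4 provides for loss in the sample size only. It arrives at 175 "considering a 10% drop out, the minimum number of study questionnaire to collect" for a 95% interval of total width 0.10 at an assumed prevalence of 10%.

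Section 3.2 lists "Availability of familiar and/or personal anamnestic data of cancer" as an inclusion criterion and "Unavailability of familiar and/or personal anamnestic data of cancer" as an exclusion criterion. Neither mentions a form that was handed out and not returned.

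**The concern.** There are two worries.

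The first is the calendar. If the 24 months is taken at face value, data collection must close on the day enrolment ends. A patient enrolled in the last four weeks could not then return the form in time. Such losses would draw on the 10% dropout allowance before any patient had died, withdrawn or forgotten the form.

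The second is selective non-return. The 10% inflation protects precision but not against bias. Patients who fail to return the form may differ in stage, performance status or family history, and the prevalence of enriched family history would then describe returners only. The visible text asks for no count of unreturned forms and no description of non-returners, although their clinical data are recorded at the first visit. A site could also read the availability criterion in Section 3.2 as letting it relabel a non-returner as ineligible, so that the loss would not appear in the report.

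**Working it through.** **Reproducing the 175.** Inputs from Section 4: prevalence 0.10, 95% confidence, total width 0.10, exact binomial method, 10% dropout. The smallest n whose Clopper-Pearson interval at x = 0.1n is no wider than 0.10 is 158 (0.058 to 0.158, width 0.0997). Allowing for dropout, 158/0.9 = 175.6, and 158 × 1.1 = 173.8. The stated 175 lies between the two and is sound.

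**Timetable.** Inputs from Sections 3.5 and 3.1: enrolment 12 months, minimum wait 28 days, analysis 12 months.

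- Stated parts: 12 + 12 = 24, leaving 0 months for the last returns.
- Minimum wait: 28/30.44 = 0.92 month.
- Shortest consistent total: 12 + 0.92 + 12 = 24.92 months. The shortfall is 0.92/24 = 3.8%.
- If the next routine visit falls at 8 weeks (an assumption): 12 + 1.84 + 12 = 25.84 months.

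**What would be lost if collection did close with enrolment.** The text does not say this; it is a worst-case assumption, together with even accrual and 175 read as patients enrolled.

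- Patients still within their four weeks: 175 × 28/365.25 = 13.4, about 13 (7.7%). With an 8-week visit: 175 × 56/365.25 = 26.8, about 27.
- Dropout allowance: 175 − 158 = 17.

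| Scenario | Forms left | Exact 95% width at 10% |
|---|---|---|
| Planned | 158 | 0.100 |
| Four-week loss only | 175 − 13 = 162 | 0.098 |
| Four-week loss, then a further 10% | 162 × 0.9 ≈ 146 | 0.104 |
| Eight-week loss, then a further 10% | (175 − 27) × 0.9 ≈ 133 | 0.109 |
| 175 read as forms actually collected | 175 | 0.0945 |

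The late-enrolment loss at the four-week minimum keeps the planned precision. The target is missed only when further loss is added, and then by 0.004 to 0.009 in total width.

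**Selective non-return.** Take 16 of 158 returners with enriched history (10.1%) and 17 non-returners with prevalence q. The prevalence in all 175 is (16 + 17q)/175.

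- q = 0.05 gives 9.6%.
- q = 0.20 gives 11.1%.
- q = 0 gives 9.1% and q = 1 gives 18.9%, the extreme bounds.

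Over the assumed range of 5% to 20%, the estimate moves by at most about 1 point, against a planned precision of ±5 points.

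**What a table of returners against non-returners could show.** For a characteristic present in half the patients, the 95% half-width of the difference is 1.96 × √(0.25/17 + 0.25/158) = 0.25, or ±25 points. Only very large differences would be visible.

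**The case for a change.** The strongest case for a change runs as follows. Sections 3.1 and 3.5 cannot both hold for a patient enrolled at the end of month 12. The primary data depend on a form returned at a later visit. All stages are eligible, so loss between visits could well be related to stage or performance status. The remedy is cheap: a few sentences, and one table from data already collected.

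Part of this stands. The sum does leave out the wait for the last forms, and the visible text makes no commitment to report how many forms were given out and how many came back. Reporting both numbers, with the first-visit characteristics of non-returners, is good practice.

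The rest does not carry. Section 3.5 ties the analysis to closure of data collection, which is a different event from the end of enrolment, and Section 3.1 gives its four weeks to each patient without exception. Losing late forms would need a closure date that the visible text does not give and that would conflict with Section 3.1. The availability criterion reads naturally as a condition of entry. Section 5 assigns sequential ID numbers to participants and Section 3.1 collects clinical data at the first visit, so the numbers enrolled and returned can be derived without a new rule. Section 3.3, the flow-chart in Section 3.4 and the appendices are not shown in the text available, so a rule on returns may exist there.

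**Conclusion.** No change to the plan is called for. The timetable point is a clerical slip: an estimated duration short by about 0.9 month at the four-week minimum, or 1.8 months if the next routine visit falls at 8 weeks (assumed). Followed as written, the study finishes later than the estimate and loses no patients or precision. Even under the contrary assumption that collection closes with enrolment, the four-week loss alone leaves the interval within the planned width.

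The point about unreturned forms is a gap that analysts fill sensibly, by stating how many forms were given out and how many came back. Writing the rule down would alter neither the primary estimate nor the 175, and a comparison with about 17 non-returners would be too imprecise to correct anything.

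The loss figures rest on even accrual and on reading 175 as patients enrolled; if 175 is the number of forms collected, precision is better than planned. The effect of selective non-return rests on the assumed 5% to 20% prevalence among non-returners. The 18.9% bound would need every one of them to have an enriched history.
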